Part B: Approach-Research Design and Methods: Having completed Specific Aims 1 and 2 in the first 18 months of this grant, we now turn to implementation of a randomized controlled trial of SMDM to evaluate Specific Aim 3.

B.1. Participants:

The planned RCT sample will consist of 166 eligible patients who receive care for type 1 diabetes at any Nemours foundation entity or at the Barbara Davis Center for Childhood Diabetes in Denver, as well as a parent or other legal caregiver of each youth. Enrollment criteria for these patients include: Age, at least 11 but not yet 18 years old, T1D for ≥ 1 year or for at least 6 months and with the most recent Hemoglobin A1c of 7.5% or higher, and facing a decision about CSII or CGM. Access to technological advances in diabetes care may be limited for racial/ethnic minorities, so we will over-sample them to enroll at least 40 youth who are self-identified racial/ethnic minorities (24% of sample). See the Section on Representation of Women and Minorities for how this will be achieved. The enrollment objectives include a minimum of 30 patients facing each treatment decision to facilitate comparisons between them.

Since preparation of the Decision Aid websites has required more time than we expected, and since the funding agency (PCORI) does not now approve no-cost extensions of their funded studies, the work must end by March 31, 2016. Therefore, the duration of follow-up for each enrolled participant will depend on the date of that participant's enrollment as follows: Enrollment before 3/31/15: 12 months; Enrollment 4/1/15 through 6/30/15: 6 months. Enrollment will end on 6/30/15 and data collection will end on 12/31/15, allowing 3 months for data cleaning and verification and completion of statistical analyses. PCORI is considering allowing no-cost extensions and if that happens, the duration of follow-up for late-enrolling participants will be extended.

Enrollment criteria are:

Inclusion Criteria for Youths: Age 11 to not yet 18 years; Physician-diagnosed T1D for at least 1 year or for at least 6 months and with the most recent Hemoglobin A_{1c} of 7.5% or higher (the minimum HbA_{1c} criterion ensures that no patients will enroll in the study who have substantial remaining endogenous insulin secretion. This will preserve the opportunity to evaluate treatment effects on HbA_{1c}, which is an important secondary outcome of the study); Considered by treating HCP to be an appropriate candidate for CSII or CGM

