Recruitment Plan C: This strategy will be used in those instances in which a family is recruited remotely. The study will be advertised with a brief description of the study in the Childrenwithdiabetes.com website. The description will include a link for more information that will take them to a study flyer within REDCap. Then if they express interest in participating in this research, the informed consent and assent forms will pop up. Families will be offered the opportunity to speak with a representative of the research team if they wish to do so before signing the consent and assent forms. The document will conclude with an electronic signature process consisting of either signing with their mouse or if using a touchpad, signing with their finger. They will have an opportunity to print the forms prior to submitting them (families that are consented electronically will also have a copy of the signed consent forms emailed to them). Prior to submitting the signed consent and assent forms, the family will complete a few contact information questions, so that a research coordinator may contact them to get them started in the study. There will be other minor modifications to the study procedures for families enrolled remotely: study visits will not need to directly coincide with clinic visits therefore can disregard references to clinic visits; participant's diabetes physician will not play a role in the study (other than to inform him/her of the participant's enrollment and to ask for copies of A1cs); a diabetes educator nurse will

not be completing the SMDM Intervention Summary Form.

[figure not shown]
Childrenwithdiabetes.com also has a couple of international Friends for Life conferences a year, in which we will also try to recruit participants both in person and by having flyers distributed to attendees of the conferences (Church Falls conference April 8-10, 2016 and Orlando conference July 5-10, 2016).

Randomization Procedures: Once a given adolescent/parent dyad completes all baseline measures, they will be randomly assigned with equal probability to one of the two study conditions described below.

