Randomization will occur at the level of patients rather than by sites or clinicians since it is the patient's behavior that is most proximal to the primary endpoints and since randomizing at the level of site or clinician runs the risk of baseline differences between groups on key clinical practices or clinician communication style. Randomization will be stratified by enrolling site so that each site randomizes a similar number of participants to UCP and SMDM. The Senior Research Coordinator in Jacksonville will compile randomization lists for each site and will manage the randomization process for all sites. We considered including an "attention placebo" control group, but decided against this due to the brief, highly structured SMDM intervention (A few extra hours over 2-4 weeks), relatively long follow-up, and difficulty in defining the precise activities that would constitute a meaningful and appropriate attention control that is not seen as transparent by the participants. The extra attention to the SMDM group is in fact the independent variable, consisting of a well-defined educational intervention. Given the limited number of eligible patients, reaching recruitment objectives for a 3-group design would be more difficult and expensive than with a 2-group design. Additional discussion of this issue appears in the Limitations section.

The decision aids developed for this study have received iterative review and feedback by a diverse group of patients and parents who have previously made decisions about CSII or CGM, by multiple Nemours HCPs who care for such patients, by two general pediatricians who are SMDM experts (Drs. [name] and [name]) and by two pediatric endocrinologists ([name], one of our external consultants and [name] who is employed part time by KidsHealth). In addition, the KidsHealth production team reflects substantial expertise in development of health care communications that are designed to harmonize with the developmental characteristics and priorities of adolescents and with the typical concerns and perspectives of parents. We believe that this combined input has yielded very high quality decision aids that are exceptionally engaging, informative and interactive guides that will help adolescent patients and their parents reach better decisions about CSII and CGM that are likely to facilitate adolescents' engagement with whichever treatment alternative they ultimately select.

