Insulin Pump and Continuous Glucose Monitor Downloads: Device downloads will be the primary outcome measures since these measures will reflect the extent to which participants demonstrate optimal use of CSII or CGM. At Visits 2 through 5, staff will download insulin pumps and CGM devices for those using them, or adolescents can e-mail data download files to the research team prior to each of those visits. For insulin pump users, the number of bolus infusions, number of times the "bolus wizard" was used and percentage of days on which fewer than 3 bolus infusions of insulin were registered will be recorded. For CGM users, the mean number of hours per day of stored CGM data will be captured from device downloads. Complete cessation of the chosen treatment will also be recorded if it occurs, which is expected to be much more common among adopters of CGM compared with adopters of CSII. Each of these scores will be transformed into z-scores relative to the full sample, permitting combined treatment of these measures in the planned analyses. Another analytic option would be to utilize an operational criterion to dichotomize patients into "Optimal" or "Suboptimal" users of CSII or CGM for the purpose of testing logistic regression models of SMDM effects. This determination will be made by [name], the project statistician.

Measures obtained at the first post-decision visit only

These measures will be obtained at the next study visit for those participants who have reached a decision. The Measurement schedule depicts this as Visit 2, which is expected to be the case for most participants, but some participants may take longer to reach a decision.

SMDM Satisfaction Scale: This measure, constructed for this study, will be completed only by adolescents and parents at the next study visit following their actual receipt and initialization of the chosen device (CGM or insulin pump). This scale is to be completed only by SMDM participants.

SMDM Satisfaction Scale- Clinician Form: This measure will be completed by clinicians at the first visit after each parent and adolescent in the SMDM group have reached a decision about the technology of interest (pump or CGM) to assess their level of satisfaction with how helpful the decision aid was for the patient/parent in the decision making process. The measure includes 5 items rated on a 5 point scale and space for the clinician to write additional comments. This will be completed for patients in the SMDM group only.

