Description of Decision Making Process: This 10-item measure asks parents and adolescents in the UC Group only to report how often they did certain activities during the decision making process and how it affected their choice, the outcome of the decision making process and how satisfied they are with their decision. This measure was constructed for this study to enable participants randomized to the UCP group to describe the process by which they made a decision about CSII or CGM. If decision making has been actively deferred, that will be treated as a decision having been made. If decision making has simply not occurred, in the absence of a definite statement to defer decision making until some point in the future, this measure will be obtained at Visits 3 and 5. Information yielded from this measure will be used primarily for descriptive purposes to enable readers to place the UCP condition in a concrete perspective.

Measures obtained at Visit 3 and Visit 5

Decision Regret Scale (DRS): The DRS is a 5-item scale for measuring a patient's degree of regret (or satisfaction) after a specific decision.¹⁶³ Items are rated on a 5-point scale ranging from "strongly agree" to "strongly disagree", and higher scores reflect more perceived regret. Internal consistency was .81 in a prior study. The scale will be completed by parents and adolescents in both the SMDM and UCP groups. Administration time is about 2-3 minutes.

SURE Test: The SURE Test is a 4-item screening tool to measure decisional conflict in patients facing clinical decisions in primary care. If the total score is less than 4, the patient is experiencing decisional conflict. The SURE Test will be completed by parents and youth in both groups at Visit 3 and at Visit 5. Administration time is about 2-3 minutes.

Measure obtained at Baseline (Visit 1) and Visit 2

Test of CSII or CGM Knowledge: Each parent and adolescent will complete a 5-item test of CSII or CGM knowledge based on content of the respective decision aids at baseline and at Visit 2 (Or the first visit after the

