Data Management and Statistical Analysis Plans The primary efficacy endpoints are indices of extent of engagement in CSII (mean number of bolus infusions/day; mean number of uses of "wizard" functions/day) or CGM use (mean number of hours of CGM use/day); and measures of decision quality (Test of CSII or CGM Knowledge; SURE Test; Decision Regret Scale; Diabetes Technology Questionnaire) at each post-decision visit. Secondary efficacy endpoints will include: HbA_{1c} measured quarterly, treatment adherence (DSMP-SR parent and youth) total scores obtained at Visits 1, 3 and 5; and Hypoglycemia Diary obtained at each quarterly clinic visit.

The Full Analysis Set will consist of all participants who provided at least one post baseline assessment record. The Completer Analysis set will include all participants who provided all post baseline primary efficacy assessment results.¹⁶⁶⁻¹¹⁶⁸ Efficacy analyses will be performed on both sets, providing both "Intention to Treat" (Full Analysis Set) and "Per-Protocol" (Completer Analysis Set) analyses. All collected data will be summarized in graphs and tables. Categorical variables will be summarized using frequencies and percentages, while quantitative variables will be described by presenting mean, median, standard deviation (or standard error of mean), minimum and maximum. Data will be summarized by group (SMDM and UCP) and type of medical decision (CSII or CGM) as well as assessment time points. Besides tabular presentation, graphical presentations of some important variables related to primary and secondary endpoints will be provided.

Assumptions for all proposed models will be checked before statistical analyses.¹⁶⁶⁻¹⁶⁸ Appropriate transformations or non-parametric methods will be used in cases of violated model assumptions. For graphical comparison of data that are sufficiently normally distributed, group means and SE of mean will be presented via bar charts. In case of substantial deviation from normality, side by side boxplots will be used for graphical comparisons. Exploratory Subgroup analyses will be conducted as needed. All tests will be performed against a two-sided alternative at the $\alpha = 0.05$ significance level and a 95% confidence interval and/or a p-value will be provided for inferential purposes. Data from all clinics will be pooled for the analyses. All analyses will be performed using the most recent version of the SAS statistical software package.

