Demographic and baseline characteristics (age, race, ethnicity, family composition, marital status, SES), primary and secondary end points, and biochemical, psychological, and behavioral variables will be summarized by intervention groups. One way analysis of variance (ANOVA) of each continuous baseline characteristic and a Fisher exact test/chi-square test/CMH test for each categorical variable will be used to compare the intervention groups at baseline. These comparisons will be used to evaluate the balance of demographic and baseline characteristics among intervention groups. Analyses of primary and secondary end points will be adjusted for significantly imbalanced baseline characteristics. For those measures completed separately by parents and youths, when parent and youth scores are correlated at $r > .70$, a combined parent-adolescent score for that variable will enter analyses. Otherwise, separate analyses will be completed on parent and adolescent scores. A mixed models (or multilevel modeling) approach will be used to test the hypotheses listed below.¹⁶⁹⁻¹⁷² The methods advocated by Holmbeck¹⁷³ will be used to evaluate baseline variables that moderate/predict SMDM-UCP treatment effects on primary study outcomes. Candidate moderator variables will include SES, youth age and gender, race/ethnicity, family structure, and health literacy and numeracy. The methods advocated by Holmbeck¹⁷³ will also be used to evaluate variables that may mediate SMDM-UCP treatment effects on primary study outcomes. In each case, these will include measures that are obtained serially and concurrently with the primary study endpoints. SAS subroutines for addressing the potential confounding influences of time- dependent covariates (e.g. youth age) will be employed as needed in these mediational analyses. With five measurement points for HbA_{1c} and hypoglycemia, the proposed mixed models approach will be capable of detecting longitudinal associations among study variables that are non-linear in form.

Hypothesis 1: Compared to UCP, the SMDM group will have significantly more favorable status in terms of indices of optimal use of CSII or CGM, scores on the CSII or CGM Knowledge Test, SURE Test, Decision Regret Scale, Diabetes Technology Questionnaire and SMDM Satisfaction Scale at each follow-up measurement point.

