Hypothesis 2: Compared to UCP, the SMDM group will have significantly more favorable status in terms of scores for treatment adherence (DSMP-SR), HbA_{1c}, and frequency of moderately severe or severe hypoglycemia at each follow-up measurement point.

Hypothesis 3: Effects of SMDM on indices of optimal use of, and satisfaction with, CSII or CGM will be mediated by changes in the measures of decision quality (Test of CSII or CGM Knowledge, Decision RegretScale, SURE Test, Decision Satisfaction Scale).

Hypothesis 4: Significant moderators of benefit from SMDM along the measured outcomes will include baseline measures of socioeconomic status, health literacy and numeracy, youth age, and family structure.

Hypothesis 5: SMDM will have indistinguishable beneficial effects on the primary study outcomes regardless of which clinical decision (CSII or CGM) was the focus of the SMDM intervention.

Statistical Power Statistical power to detect treatment effects of interest on the primary endpoints was assessed using the online DSS Research Statistical Power Calculator.¹⁷⁴ With enrollment of 166 eligible youth and parents and attrition of 10% over the 12-month study, and a resulting “Completer” sample size of 150, the study will have statistical power of .87 to detect a moderate treatment effect of ~0.4 SD on the measures of decision quality and CSII or CGM optimal use. Even though statistical power remains adequate for detection of somewhat smaller treatment effects, effects of less magnitude are unlikely to have sufficient clinical significance to warrant the added cost and inconvenience of implementing SMDM.

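### Decision type (CSII, CGM or both) is known before randomization but is not a prespecified term in the Hypothesis 1 and 2 models; adding it is a cheap precision gain of uncertain size

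*Combined protocol and SAP*

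**What the plan says.** **Randomization.** Section B.1 (Randomization Procedures) provides one list per site, with families "randomly assigned with equal probability to one of the two study conditions". Section B2 repeats the site stratum: "Randomization will be stratified by enrolling site so that each site randomizes a similar number of participants to UCP and SMDM". No other stratum is named. Randomization follows completion of all baseline measures.

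**Decision type at baseline.** Section B.3 says "Each parent and adolescent will complete a 5-item test of CSII or CGM knowledge based on content of the respective decision aids", first at baseline and again at Visit 2 or the first post-decision visit. The device under consideration is therefore known before allocation. The equivalent forms described there separate visits and respondents; nothing equates the CSII test with the CGM test. The DTQ, also in B.3, rates whatever package of technology the family is using. Sections B.1 and B2 allow a youth to be a candidate for both devices, at once or in sequence.

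**Analysis.** Section B.5 specifies mixed models without listing fixed effects. Its covariate rule is "Analyses of primary and secondary end points will be adjusted for significantly imbalanced baseline characteristics". Decision type appears in B.5 as a descriptive breakdown and in Hypothesis 5, which compares the SMDM effect across the two decisions. Section B.1 adds "The enrollment objectives include a minimum of 30 patients facing each treatment decision to facilitate comparisons between them". Standardization is stated only for device-use scores, each converted to a z-score before combining (B.3, device downloads).

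**The concern.** A baseline variable that predicts outcome belongs in the model whether or not the arms happen to differ on it. Here the Knowledge endpoint combines two different 5-item tests, and a difference in their difficulty would go into the error variance unless the model removes it. The DTQ may differ by decision because the devices differ.

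Selecting covariates by a baseline significance test is a weak substitute. When the arms are balanced the variable stays out and the precision gain is lost. When the imbalance is moderate but not significant it also stays out, and the realized estimate moves with the mix. The rule also makes the Hypothesis 1 and 2 models depend on the data.

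At stake is precision on the questionnaire endpoints, in a trial whose recalculated power at the stated effect leaves little to spare.

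**Working it through.** **Inputs from the documents:** 166 enrolled, 10% attrition, 150 completers (taken as 75 per arm), two-sided 0.05, effect about 0.4 SD (B.5, Statistical Power); at least 30 families per decision (B.1).

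**Assumptions:** the mean outcome gap g between CSII and CGM families is not given; 0.2 to 1.0 total SD is used. The mix runs from 30 of 166 (share p = 0.18) to p = 0.50. Dual candidates are ignored here. The comparison is a single follow-up measurement with no baseline adjustment.

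**Step 1. The plan's own figure.** B.5 states "the study will have statistical power of .87 to detect a moderate treatment effect of ~0.4 SD". Power = Φ(d/√(2v/n) − 1.96), with v the residual variance. With d = 0.4, n = 75 and v = 1: 0.4/√(2/75) = 2.449, and Φ(0.489) = 0.688 (0.682 by the noncentral t). The stated .87 does not reproduce; 0.5 SD would give 0.865. That is a separate matter, and 0.688 is the reference below.

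**Step 2. Power with the term.** Taking 0.4 SD as a total SD, the term removes p(1−p)g², so v = 1 − p(1−p)g². Here p(1−p) is 0.148 at 30:136 and 0.25 at 50:50.

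| Assumed gap g | v, 30:136 | Power | Gain (points) | v, 50:50 | Power | Gain (points) |
|---|---|---|---|---|---|---|
| 0.2 SD | 0.994 | 0.690 | 0.3 | 0.990 | 0.692 | 0.4 |
| 0.5 SD | 0.963 | 0.704 | 1.6 | 0.938 | 0.716 | 2.8 |
| 1.0 SD | 0.852 | 0.756 | 6.8 | 0.750 | 0.807 | 12.0 |

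**Step 3. What the conditional rule would catch.** With 83 per arm, the difference in shares has standard error √(2p(1−p)/83): 0.0597 at 30 families and 0.0776 at 83.

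- 30 families: a 19:11 split differs by 8/83 = 9.6 points (z = 1.61, not adjusted); 20:10 differs by 12.0 points (z = 2.02, adjusted).
- 83 families: 47:36 differs by 13.3 points (z = 1.71, not adjusted); 48:35 differs by 15.7 points (z = 2.02, adjusted).

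This is the uncorrected chi-square test. Fisher's exact test, which the plan also names, is more conservative and would need a wider split. With fixed equal arms, a difference of 10 points or more has probability 0.07 (30 families) to 0.21 (50:50). An unadjusted 13.3-point difference would move the estimate by 0.133 × 0.5 = 0.07 SD for a 0.5 SD gap. Such shifts are how the variance in Step 2 shows up in a single trial; they are not an additional loss.

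**The case against.** Five points on the other side carry weight.

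- **Silence is not exclusion.** B.5 lists no fixed effects for any hypothesis, not even site. Hypothesis 5 cannot be tested on the primary outcomes in a mixed model without decision type and its interaction with group. A reader might infer that the plan pools these endpoints deliberately without decision type; the documents do not say so. What stands is that nothing requires the term for Hypotheses 1 and 2, and the secondary endpoints have no planned decision-type comparison.

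- **Device use is largely protected.** Bolus and wizard counts exist only for pump users and CGM hours only for CGM users, so z-scoring each measure centres each device near zero. The remark about complete cessation, "which is expected to be much more common among adopters of CGM compared with adopters of CSII", does not by itself show a mean gap on these scores. Handling of cessation and of users of both devices remains open.

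- **Baseline values may do part of the work.** Knowledge and the DTQ are measured at baseline, and a model using those values would absorb much of a stable gap. The plan does not say it will. SURE and Decision Regret have no baseline, but they are the same scales for both decisions.

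- **Power is not cut from a planned level.** Treating 0.4 SD as a within-decision SD would give a fall from 0.68 to 0.59 at a 1.0 SD gap and a 50:50 mix. The plan does not define its SD that way. On the ordinary reading the term adds power.

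- **Stratified lists are a doubtful remedy.** Four Nemours facilities, Denver and remote families, if listed separately, times three categories make 18 strata for 166 families, about nine each. Small blocks would make allocation easier to predict. A 20:10 split of a 30-family group raises its standard error only 6% over 15:15, since √((1/20 + 1/10)/(2/15)) = 1.06.

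**Conclusion.** The point holds as an inexpensive improvement to the analysis. Decision type is known at baseline and plausibly prognostic for the questionnaires, and the significance-based covariate rule is a poorer method than a prespecified term. On the assumptions above, the gain is under 1 point of power at a 0.2 SD gap, about 2 to 3 at 0.5 SD, and 7 to 12 at 1.0 SD. It would be smaller for Knowledge and the DTQ if baseline values enter the model.

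A reader might infer that the SMDM effect is biased, that type I error is inflated, or that the site-only lists are faulty. The documents support none of these. Chance imbalance under randomization costs precision only, and site stratification is acceptable at this sample size.

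**What to change.** In B.5, specify that every Hypothesis 1 and 2 model includes decision type at randomization (CSII, CGM, both) as a fixed effect, whatever the baseline balance tests show. Classify each family by the decision faced at randomization, and do not reclassify those who later consider the second device. Standardize Knowledge scores within the CSII or CGM version, using both arms together, before pooling; state how a family that takes both versions is handled.

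The cost is SAP wording and 1 to 2 degrees of freedom, with no new data to collect. Stratifying the lists by decision type is optional and not required, given the small strata and the youths who are candidates for both devices.
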